### **12.3 Stratification Factors**

Patients will be stratified based on severity of disease as measured by PASI scores <12 or  $\geq 12$  at screening. Within each stratum, patients will be randomized at 1: 1 ratio to the two treatment arms using permuted block randomization with varying block size.

### **12.4 Analysis of Endpoints**

#### **12.4.1 Analysis of Primary Endpoints**

The primary endpoint is the week 16 PASI score. We will calculate the percent reduction in week 16 PASI scores post treatment from baseline. Summary statistics in terms mean, standard deviation, median and range or inter-quartile range will be generated for each study arm. Between treatment arm differences will be evaluated using a two-sample t-test or the non-parametric Wilcoxon rank sum test where appropriate. The primary analysis will be carried out on an intention-to-treat basis. Last value carried forward will be used to impute for patients missing week 16 measurements. Per-protocol analysis will also be carried out among patients who are deemed compliant to treatment (defined as at least 75% of doses taken as measured by pill counts) and had both baseline and week 16 measurements will also be carried out using similar statistical methods. P-values less than 0.05 will be considered statistical significant.

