### **1.2.4 Primary Endpoints**

1. PASI instrument score.

Assessments will be made at baseline and every 2 weeks for 20 weeks.

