### **12. Statistical Considerations**

#### **12.1 Study Design/Endpoints**

This is a randomized, double-blind, placebo-controlled phase II study to examine the efficacy of rimegepant, an orally available competitive inhibitor of the CGRP receptor, in patients diagnosed with psoriasis. Patients in each strata of disease severity as defined by baseline PASI score (<12, or >=12) will be randomized at 1:1 ratio to receive 16-week treatment of either rimegepant or placebo. The primary endpoint includes the percent reduction in PASI score post-treatment measured at week 16 from baseline defined as  $100\% \times (\text{PASI.pre-PASI.post})/\text{PASI.pre}$ . Secondary endpoints include PASI50, an indicator of whether a patient had at least 50% improvement in PASI score at week 16 post-treatment compared to baseline, the reduction (i.e., the difference) in the Investigator's Global Assessment (IGA) score post treatment from baseline, change in Dermatology Quality of Life Index (DQLI) at week 16 post treatment compared to baseline, change in Itch Score post treatment from baseline, and the overall patterns of change in PASI scores, IGA scores and DQLI scores measured longitudinally.

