#### **12.2 Sample Size/Accrual Rate**

The primary objective of the study is to examine if patients receive the rimegepant treatment had greater improvement in psoriasis in terms of the primary endpoints compared to patients received the placebo. The primary endpoints include both the percent reduction in PASI score post-treatment from baseline and the change IGA score post-treatment from baseline.

The sample size is determined to ensure adequate power to detect clinically meaningful differences in the co-primary endpoints between the treatment arms. With a sample size of 30 patients (15 per treatment arm), we will have 80% power to detect an effect size as small

as 1.06 using a two-sample t-test at a two-sided significance level of 0.05 for each of the primary endpoint. This level of effect size corresponds to >21% differences in the percent reduction in PASI scores post treatment from baseline between the two treatment arms assuming the standard deviation of the percent reduction in PASI score is about 20% which is likely to be a conservative estimate based on published results from trials in patients with moderate to severe disease. This level of effect size also corresponds to a difference of 0.5 in the change of IGA scores between the two study arms assuming the standard deviation of change is around 0.5. Accounting for a dropout rate of 25% a total of 45 patients will be recruited.

The study expects to accrue 5 patients per month and accrue all study patients within 6-10 months.

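### The primary endpoint is stated inconsistently: only percent PASI reduction at week 16 has power inputs among the PASI wordings, and IGA change is co-primary in Section 12.2 but secondary elsewhere

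*Combined protocol and SAP*

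**What the plan says.** The combined protocol and SAP describes the primary endpoint in five places.

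- **Sections 1 and 1.2.4** name the PASI instrument score and add only a schedule: "Assessments will be made at baseline and every 2 weeks for 20 weeks". They give no analysis time point and no summary measure.
- **Section 12.1**: "The primary endpoint includes the percent reduction in PASI score post-treatment measured at week 16 from baseline", followed by a formula. IGA is listed among the secondary endpoints, as "the reduction (i.e., the difference) in the Investigator's Global Assessment (IGA) score post treatment from baseline".
- **Section 12.2**: "The primary endpoints include both the percent reduction in PASI score post-treatment from baseline and the change IGA score post-treatment from baseline". It calls these co-primary and claims 80% power for each.
- **Section 12.4.1** opens with "The primary endpoint is the week 16 PASI score". Its next sentence is "We will calculate the percent reduction in week 16 PASI scores post treatment from baseline". Summary statistics and a between-arm t-test or Wilcoxon test follow.

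Section 1 (secondary endpoints) and Section 12.4.2 also treat IGA as secondary. The pattern of PASI over time is an exploratory objective in Section 1.2.3, but longitudinal PASI patterns are among the secondary endpoints in Section 12.1.

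**The concern.** A primary endpoint needs a variable, a time point and a summary measure, stated once. Here the front sections omit the last two, the analysis section names one variable and computes another, and the sample size section adds a second endpoint.

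Two things are at stake. First, a raw week 16 PASI score and a percent reduction are different variables. Entry requires PASI of at least 5 with no upper limit (Section 4.2), and randomization is stratified at 12 (Section 12.3), so the plan expects baselines to vary. Section 12.4.1 does not adjust for baseline. A raw score would carry the baseline spread that percent reduction scales out, and the two tests could disagree in a 30-patient trial.

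Second, whether IGA change is primary decides which tests determine success, and Section 12.2 gives no rule on whether one or both must succeed. Section 7.11 leaves the statistician unblinded, which is a further reason to leave no choice of primary variable open.

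**Working it through.** **1. The plan's own figure.** Section 12.2 supplies: "With a sample size of 30 patients (15 per treatment arm"), a standardized effect of 1.06, a two-sample t-test, two-sided alpha 0.05 and 80% power. With n1 = n2 = 15:

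- degrees of freedom = 15 + 15 - 2 = 28
- noncentrality = d x sqrt(n1 n2/(n1 + n2)) = 1.06 x sqrt(225/30) = 1.06 x 2.739 = 2.90
- power from the noncentral t distribution = **80.0%**

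The detectable effect at 80% power is 1.060, so the stated figure reproduces.

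**2. Percent PASI reduction.** The inputs are a difference above 21 percentage points and an SD stated as "assuming the standard deviation of the percent reduction in PASI score is about 20" percent. The effect 1.06 corresponds to 1.06 x 20 = 21.2 points. At 21.2/20 = 1.06 power is 80.0%; at exactly 21/20 = 1.05 it is 79.3%. The claim holds for this variable.

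**3. IGA change.** The inputs are a difference of 0.5 and an SD of about 0.5, so d = 0.5/0.5 = 1.00, not 1.06. The noncentrality is 2.739 and power is **75.3%**. The t-test would need 17 per arm to reach 80% at d = 1.00.

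If IGA did stay co-primary, the missing decision rule would matter:

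- Both endpoints required: joint power is at most 75.3%, and 0.800 x 0.753 = 60.2% if the two are independent.
- Either sufficient, each at 0.05: familywise error is 1 - 0.95² = 9.75% if the two are independent.

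**4. Raw week 16 PASI.** The documents give no mean, difference or SD on this scale, so no power figure can be taken from them. What follows is illustration only. Set week 16 PASI = baseline x (1 - percent reduction/100), with percent reduction normal, SD 20, and arms 21.2 points apart. The baseline distributions and placebo mean reductions are assumptions. There were 40,000 simulated trials per scenario, 15 per arm, with an unadjusted t-test.

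| Assumed baseline PASI | Placebo mean 0% | 10% | 20% |
|---|---|---|---|
| All equal (8) | 80% | 80% | 80% |
| Uniform 5-12 | 47% | 51% | 56% |
| Uniform 5-20 | 31% | 36% | 41% |

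Over placebo means of 0-25%, the two uniform cases span about 31-59%. A right-skewed baseline (5 plus an exponential with mean 5) gives 21-35% over placebo means of 0-30%. Percent reduction stays at 80% throughout.

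**5. Reading the PASI statements together.** The second sentence of Section 12.4.1, the formula in Section 12.1 and the power inputs in Section 12.2 all point to percent reduction. Section 12.1 and both sentences of Section 12.4.1 fix week 16. Sections 1 and 1.2.4 are silent on both points.

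**The case against.** The best defense is that the intended endpoint can be recovered. Section 12.4.1 moves at once from the week 16 score to percent reduction, and its test follows that sentence; Section 12.1 gives the formula; Section 12.2 sizes the trial on it. That stands, and it rules out several stronger readings that a reader might infer:

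- *That the PASI wordings are rival, incompatible endpoints.* Sections 1 and 1.2.4 are underspecified. They give an instrument and a visit schedule, and do not define a repeated-measures endpoint that includes the off-drug visits at weeks 18 and 20.
- *That the trial has only 31-59% power.* No section specifies a between-arm test of raw PASI. The range rests wholly on assumed baselines and placebo means, ignores the stratification at 12, and its uniform 5-12 case leaves the upper stratum essentially empty.
- *That 80% power can hold only for percent reduction, or that Section 12.2 powers nothing else.* Any t-tested endpoint with a standardized effect of 1.06 has 80% power at this size, and Section 12.2 makes the claim for IGA too.

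On IGA, it can be said that 0.5 may be a rounding of 1.06 x 0.5 = 0.53, at which 80% would hold. The document does not say so, and the inputs as printed give 75.3%.

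None of this removes the defect. The reader must infer the primary variable, and no such inference settles IGA, because Section 12.2 directly contradicts Sections 1, 12.1 and 12.4.2.

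**Conclusion.** The point holds as one of inconsistent specification. The statistical sections favor percent reduction in PASI at week 16, but the front sections do not state it and the analysis section opens by naming something else. Among the PASI wordings, the power statement supports percent reduction alone (80.0% at 21.2/20 = 1.06, 15 per arm). Power for a raw score is unsupported. It would be lower if baseline PASI varies, but by an amount that depends on assumptions outside the documents.

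The sharper conflict is over IGA change: co-primary with 80% power claimed in Section 12.2, secondary elsewhere, and 75.3% power on the printed inputs. That figure uses only the document's numbers and the stated t-test.

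**What to change.** - Put one sentence, identically worded, in Sections 1, 1.2.4, 12.1, 12.2 and 12.4.1: *The primary endpoint is the percent reduction in PASI from baseline (Day 0) to Week 16.* Naming Day 0 is useful because PASI is also scored at screening; Section 6.1.2.1 already labels the Day 0 visit as baseline.
- Delete "The primary endpoint is the week 16 PASI score" from Section 12.4.1.
- In Section 12.2, make IGA change secondary, in line with the other sections. Remove its 80% power claim or restate it as about 75%.
- Place the longitudinal PASI pattern in one tier, secondary or exploratory, in both Sections 1.2.3 and 12.1. The two-weekly assessments through week 20 then serve that analysis.

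The cost is a wording amendment. Visits, data collection and the planned tests do not change.

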#### Blinding and Unblinding Method

- Patients and all clinical evaluators will be blinded to treatment assignment.
- The Statistician and the Study Pharmacist at the participating sites will not be blinded to treatment assignment.
- Study assignments will be unblinded to the Study Investigators and Coordinators after all of the data are collected, the study database has been locked, and analyses are completed.
- Emergency unblinding will occur if the participant's physician deems that unblinding is necessary, such as in the case of unacceptable toxicity thought to be related to the study agent or progressive disease.
- The Independent Medical Monitor will also be blinded unless unblinding is warranted (if the participant's physician deems that unblinding is necessary, or after all of the data are collected and the study database has been locked).
- The date and reason for breaking the blind must be documented in the study database.

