#### **12.4.2 Analysis of Secondary Endpoints**

Quantification of subjects in each arm achieving PASI50 at week 16, defined as achieving  $\geq 50\%$  reduction in PASI scores measured at week 16 post treatment from baseline, will be summarized. Summary statistics including count and proportion in each treatment arm will be provided for patients enrolled in each arm. Differences in proportions between treatment arms will be summarized along with 95% confidence interval. Exploratory comparison will be carried out using Fisher's exact test.

For change in IGA scores at week 16 post treatment from baseline, summary statistics in terms mean, standard deviation, median and range or inter-quartile range will be generated for each study arm. Between treatment arm differences will be evaluated using a two-sample t-test or the non-parametric Wilcoxon rank sum test where appropriate.

For change in DQLI scores at week 16 post treatment from baseline, summary statistics in terms mean, standard deviation, median and range or inter-quartile range will be generated

for each study arm. Between treatment arm differences will be evaluated using a two-sample t-test or the non-parametric Wilcoxon rank sum test where appropriate.

For change in Itch Scores at week 16 post treatment from baseline, summary statistics in terms mean, standard deviation, median and range or inter-quartile range will be generated for each study arm. Between treatment arm differences will be evaluated using a two-sample t-test or the non-parametric Wilcoxon rank sum test where appropriate.

For longitudinal measurements of the study endpoints obtained overtime, patterns of differences between treatment arms will be evaluated using linear mixed-effects or generalized linear-mixed effects models.

For all these study endpoints, the primary analysis will be carried out on an intention-to-treat basis. For endpoints concerning change at week 16 from baseline, a conservative method for imputation such as last-value carried forward will be used for those missing measurements at week 16. For analysis concerning longitudinal data, no missing imputation will be applied. Secondary per protocol analyses will also be carried out among patients who complied to study treatments.

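### Week-16 scores are compared without adjustment for the PASI stratum or baseline score, which forgoes precision if these predict outcome

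*Combined protocol and SAP*

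**What the plan says.** - **Randomisation.** Section 12.1: "Patients in each strata of disease severity as defined by baseline PASI score (<12, or >=12) will be randomized at 1:1 ratio". Section 12.3 repeats this with the screening score: "Patients will be stratified based on severity of disease as measured by PASI scores <12", or 12 and above. Section 7.11 also uses the screening score.
- **Baseline data.** The Schedule of Assessments (6.1) and the Visit 1 list (6.1.2.1) have PASI, IGA, DLQI and itch scored at Day 0.
- **Primary endpoint.** Section 12.1: "The primary endpoint includes the percent reduction in PASI score post-treatment measured at week 16 from baseline".
- **Primary test.** Section 12.4.1: "Between treatment arm differences will be evaluated using a two-sample t-test or the non-parametric Wilcoxon rank sum test where appropriate". Section 12.4.2 uses the same sentence for the week-16 changes in IGA, DLQI and itch.
- **Longitudinal data.** Section 12.4.2 adds that "patterns of differences between treatment arms will be evaluated using linear mixed-effects or generalized linear-mixed effects models". No covariates are listed, and these models do not replace the week-16 test.
- **Power.** Section 12.2 claims 80% power with 15 per arm for an effect size as small "as 1.06 using a two-sample t-test at a two-sided significance level of 0.05 for each of the primary endpoint".
- **Blinding.** Section 7.11: "The Statistician and the Study Pharmacist at the participating sites will not be blinded to treatment assignment".

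No section plans an adjusted or stratified between-arm test of these week-16 scores.

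**The concern.** The design balances the arms on PASI severity and the analysis then ignores it. If stratum or baseline score predicts outcome, two things follow. The ordinary two-sample standard error still contains variation that stratification has already balanced between arms, so it is too large and the test rejects too rarely. And outcome variation that the Day 0 score could explain stays in the error term.

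Neither makes a positive result wrong. The risk is of missing a real effect, or estimating it less precisely than the collected data allow. That matters in a trial whose unadjusted test reaches 80% power only for a difference above one standard deviation.

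A smaller, separate point is that the choice between t-test and Wilcoxon has no stated criterion and falls to an unblinded statistician.

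**Working it through.** **Inputs from the plan (12.2).** 15 per arm, two-sided alpha 0.05, effect size d = 1.06, SD of percent PASI reduction 20%.

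**Assumed, because the documents give no figure.** Within-arm correlation ρ between Day 0 PASI and percent reduction, 0 to 0.5. Screening and Day 0 PASI correlated 0.95. Upper stratum 50% or 20% of patients. Permuted blocks of 2 and 4. Normal, complete data.

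**1. The plan's own figure.** Two-sample t-test with df = 28 and noncentrality d√(n/2) = 1.06 × √7.5 = 2.90. Power is 0.800. In PASI units, 1.06 × 20 = 21.2 points, matching the plan's figure of more than 21%. The stated power is correct and belongs to the unadjusted test.

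**2. One baseline covariate, by formula.** Residual SD = SD × √(1 − ρ²). Allowing for chance covariate imbalance multiplies the variance by 1 + 1/27, and df = 27. At ρ = 0.5 the effective effect size is 1.06 / (0.866 × 1.018) = 1.20.

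| ρ | Power | Difference detectable with 80% power (points) |
|---|---|---|
| 0 | 78.4% | 21.6 |
| 0.2 | 80.0% | 21.2 |
| 0.3 | 82.1% | 20.6 |
| 0.4 | 85.0% | 19.8 |
| 0.5 | 88.7% | 18.7 |

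The unadjusted test is at 80.0% and 21.2 points, so break-even is at ρ of about 0.20.

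**3. The full model, by simulation.** 20,000 trials per setting with stratified block randomisation. The adjusted model has arm, stratum and Day 0 PASI. Power and test size are ranges over the two stratum splits; interval widths are for the 50% split, at SD 20%.

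| ρ | Power unadjusted | Power adjusted | True size of unadjusted test | Mean 95% CI width, unadjusted → adjusted (points) |
|---|---|---|---|---|
| 0 | 80% | 78% | 4.9–5.2% | 29.7 → 30.4 |
| 0.3 | 80% | 82% | 4.6% | 29.7 → 28.9 |
| 0.4 | 80–81% | 85% | 4.1–4.5% | 29.7 → 27.8 |
| 0.5 | 80–81% | 88% | 3.4–4.1% | 29.7 → 26.2 |

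The adjusted test's size stayed at 4.8 to 5.2%. The interval at ρ = 0.5 is 1 − 26.2/29.7 = 12% narrower.

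**4. Change scores (IGA, DLQI, itch).** If the variance is equal at baseline and week 16 (assumed) and r is the correlation between the two, then |corr(change, baseline)| = √((1 − r)/2). At the same benchmark, d = 1.06:

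| r | Correlation of change with baseline | Power unadjusted | Power adjusted for stratum and own baseline |
|---|---|---|---|
| 0.8 | 0.32 | 80% | 82% |
| 0.7 | 0.39 | 80% | 84–85% |
| 0.5 | 0.50 | 80% | 88–89% |

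The ranges cover an own baseline uncorrelated with PASI and one correlated 0.5 with it. The result is approximate for the ordinal IGA.

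**The case against.** - **The plan is valid and consistent.** The named test is the one the sample size was built on, and this is a pilot. That stands: the point is efficiency, not error.
- **The gain rests on an unknown correlation.** Percent reduction already divides by baseline PASI, so what correlation remains may be small. Below about 0.2 a covariate gains nothing, and the two-covariate model can lose about 2 points. This also stands, and it is the main uncertainty. Still, dividing by baseline does not guarantee a zero correlation, and under the equal-variance assumption the change scores are above break-even at every pre–post correlation tried.
- **80% is not the plan's power for every score.** For IGA, section 12.2's difference of 0.5 with SD 0.5 gives d = 1.0 and power of 75%, although the same section claims 80% for each primary endpoint and counts IGA among them. DLQI and itch have no stated power. The 80% in the change-score table is therefore a common benchmark only.
- **The number of patients is unclear.** Section 12.2 recruits 45 and the Protocol Summary enrols 30. If 45 were randomised and analysed by intention to treat, unadjusted power would be 93.5% and the power gain only about 1 point at correlation 0.3 and 3 points at 0.5. The interval would still narrow by a similar proportion.
- **Stratum and Day 0 PASI overlap.** With 30 patients, Day 0 PASI alone gave about 1 point more power than both terms together (82.8% against 81.7% at 0.3). Keeping the stratum makes the analysis follow the randomisation, for a small price.

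**Conclusion.** The concern holds as a conditional loss of efficiency. The omission is certain; the size of the loss is not. For the primary endpoint with 15 per arm and d = 1.06, the proposed model changes power by about −2 points at correlation 0, +1 at 0.3, +4 at 0.4 and +7 to +8 at 0.5. The unadjusted test stays valid and becomes conservative as the correlation grows. These figures rest on the assumed correlations and on complete, normally distributed data; percent reduction is capped at 100%, and last-value imputation is planned. At most about 2 points are at risk and up to 8 may be gained, for a change of wording. This should be changed, but the trial's validity does not depend on it.

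**What to change.** **Section 12.4.1.** Name one primary test: an analysis of covariance of week-16 percent PASI reduction with terms for arm, randomisation stratum as used at allocation (screening PASI below 12, or 12 and above) and continuous Day 0 PASI. Report the adjusted difference with its 95% confidence interval. Name a Wilcoxon test stratified by randomisation stratum (van Elteren) as the sensitivity analysis. This also closes the open choice between t-test and Wilcoxon.

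**Section 12.4.2.** Use the same approach for change in IGA, DLQI and itch, each with its own Day 0 score as the covariate.

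**Timing.** Fix the model before any outcome is examined by arm, because adjustment added later would be open to challenge as data-driven.

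**Cost.** SAP wording, two model degrees of freedom, and up to about 2 points of power if baseline is unrelated to outcome. A model with Day 0 PASI alone would recover about 1 point but leave out the stratum. No new data, visits or patients are needed.

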**Primary Endpoints:**

1. PASI instrument score  
Assessments will be made at baseline and every 2 weeks for 20 weeks.

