### **8. Study Intervention Discontinuation and Participant Discontinuation/Withdrawal**

#### **8.1 Discontinuation of Study Intervention**

Subjects will be withdrawn from study treatment permanently for the following reasons:

1. Development of any hypersensitivity phenomena that may be related to the study medication.
2. Excessive nausea making continuation of participation in the study impossible.
3. Development of any intercurrent illness or medical need to take a medication such that exclusion criteria apply.
4. Occurrence of pregnancy in a female subject.
5. If any clinical adverse event (AE), laboratory abnormality, or other medical condition or situation occurs such that continued participation in the study would not be in the best interest of the participant
6. Disease progression which requires discontinuation of the study intervention
7. If the participant meets an exclusion criterion (either newly developed or not previously recognized) that precludes further study participation

Subjects will be referred for appropriate medical care for any adverse effects.

Subjects will continue to be followed for assessment of disease severity until the 20-week period is over.

Discontinuation of treatment does not mean discontinuation from the study, and remaining study procedures (assessments of disease severity) will be completed as indicated by the study protocol.

If a clinically significant finding is identified (including, but not limited to changes from baseline) after enrollment, the investigator or qualified designee will determine if any change in participant management is needed. Any new clinically relevant finding will be reported as an adverse event (AE).

**Criteria for interrupting the study:** We will have a study monitoring committee (SMC) consisting of the study PI, the medical monitor and 1 investigator not directly involved in the conduct of this study. This committee will review all Grade 3 or 4 events, and all SAEs in real time. We will pause enrollment of new participants if there is 1 or more Serious Adverse Events that are at least possibly related to study drug, or 2 or more Grade 3 or 4 events at least possibly related to study drug. The enrollment of participants will not resume until the SMC reviews the adverse events and agrees unanimously to resume enrollment.

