## 8.2 Participant Discontinuation/Withdrawal from the Study

Participants are free to withdraw from participation in the study at any time upon request. An investigator may discontinue or withdraw a participant from the study for the following reasons:

1. Pregnancy. However, subjects will be followed until the end of the pregnancy.
2. Significant study intervention non-compliance (failure to take medications, refuses to allow study procedures).
3. Participant lost to follow-up after 3 attempts to contact subject to schedule study visit.

The reason for participant discontinuation or withdrawal from the study will be recorded on the Case Report Form (CRF). Subjects who sign the informed consent form and are randomized but do not receive the study intervention may be replaced. Subjects who sign the informed consent form, and are randomized and receive the study intervention, and subsequently withdraw, or are withdrawn or discontinued from the study will not be replaced.

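### LOCF is the only rule for a missing week 16 PASI in the primary analysis and is elsewhere called conservative, but its bias has no fixed direction; a week 16 mixed-model contrast should be pre-specified

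*Combined protocol and SAP*

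**What the plan says.** Section 12.4.1 makes the primary analysis intention-to-treat, tests percent PASI reduction at week 16 with a two-sample t-test or Wilcoxon test, and gives one rule for missing values: "Last value carried forward will be used to impute for patients missing week 16 measurements". The only other analysis there is per-protocol. It needs an observed week 16 value and 75% compliance, so it leaves out the patients for whom the rule matters.

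Section 12.4.2 covers the secondary week 16 change endpoints: "a conservative method for imputation such as last-value carried forward will be used for those missing measurements at week 16". For repeated measurements it says that "patterns of differences between treatment arms will be evaluated using linear mixed-effects or generalized linear-mixed effects models", and "For analysis concerning longitudinal data, no missing imputation will be applied". It names no week 16 contrast, no covariance structure and no role for these models as a check on the primary result.

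The data for such a contrast are already being collected. On PASI, the Protocol Summary says: "Assessments will be made at baseline and every 2 weeks for 20 weeks". Section 8.1 says of patients who stop study drug: "Subjects will continue to be followed for assessment of disease severity until the 20-week period is over". Missing week 16 values should therefore come mainly from patients who leave the study. Section 8.2 allows the investigator to withdraw patients for significant non-compliance, and says of treated patients that those who leave "and subsequently withdraw, or are withdrawn or discontinued from the study will not be replaced". Section 12.2 assumes 25% dropout overall and gives no split by arm.

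**The concern.** LOCF treats the PASI at a patient's last visit as the week 16 value. If patients are still improving when they leave, their improvement is understated. What this does to the between-arm difference depends on how many leave each arm, when they leave, and how fast each arm is changing. None of this is known in advance, so no general statement that LOCF errs on the safe side can be supported.

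At stake is how the primary estimate is read. A reader who takes the method to be conservative may over-trust a positive result when placebo lost more patients, or read a diluted difference as a lack of effect. With 30 patients and 25% dropout, about 30 x 0.25 = 7.5 week 16 values would be carried forward, and no planned analysis is identified to show how much the result depends on them.

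**Working it through.** **The plan's own figure.** Section 12.2: 15 per arm, effect size 1.06, two-sided 0.05, two-sample t-test. The noncentral t distribution gives power 0.800, as stated. With the plan's SD of 20, the difference is 1.06 x 20 = 21.2 points.

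**Assumptions not in the documents.** The eight visits run from week 2 to week 16. A dropout's last visit is equally likely to be any of weeks 2 to 14 and is unrelated to response. Mean improvement is either linear to week 16, or linear to week 8 and then flat. All randomised patients are kept. The simulations add within-patient correlation 0.7 and an SD that is either 20 throughout or rises from 10 to 20.

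**Expected LOCF mean in one arm** = m x (1 - d x u), where m is the true week 16 mean, d the dropout rate and u the share of the improvement not yet seen at exit.
- Linear: mean last visit is week 8, so u = 1 - 8/16 = 0.50.
- Plateau: the shares seen are 0.25, 0.50, 0.75, 1, 1, 1, 1, with mean 5.5/7 = 0.786, so u = 0.214.

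**True difference 21.2.** For 25/25, linear: 21.2 x (1 - 0.25 x 0.50) = 18.55. Plateau: 21.2 x (1 - 0.25 x 0.214) = 20.06. For unequal dropout the answer depends on the assumed means:

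| Means, active / placebo | Dropout %, active / placebo | LOCF, linear | LOCF, plateau |
|---|---|---|---|
| either pair below | 25 / 25 | 18.5 | 20.1 |
| 41.2 / 20 | 35 / 15 | 15.5 | 18.8 |
| 21.2 / 0 | 35 / 15 | 17.5 | 19.6 |
| 41.2 / 20 | 15 / 35 | 21.6 | 21.4 |
| 21.2 / 0 | 15 / 35 | 19.6 | 20.5 |

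With the same 15/35 dropout, LOCF lands just above the truth for one pair of means and below it for the other.

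**No drug effect.** Bias towards active = m x u x (placebo dropout - active dropout).
- 25/25: zero; simulated rejection 5%.
- 10/40, both arms improving 20: 20 x 0.30 x 0.50 = 3.0 (linear) or 20 x 0.30 x 0.214 = 1.3 (plateau); simulated rejection about 5-7%.
- 10/40, both improving 30: 4.5 or 1.9; rejection 6-10%.
- 40/10: the same sizes with the sign reversed.

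**Mixed model, week 16 contrast.** This was simulated with arm-by-visit means, heterogeneous compound symmetry and Kenward-Roger degrees of freedom, without covariates. At 25/25 it estimates 21.2 with power 74% (72% if the true correlation is AR(1)). LOCF power is 62-73% (linear) or 72-80% (plateau), against 80% with complete data. Null rejection was 4.3-5.8% over 25/25, 15/35 and 10/40. The covariance matters: homogeneous compound symmetry rejected a true null in 15% of runs at 25/25 when the SD rose from 10 to 20, while the heterogeneous form rejected 5%.

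A separate simulation used AR(1) correlation 0.85, linear change, smaller mean reductions and, in most scenarios, poorer responders leaving more often. LOCF bias ran from -6.9 to +3.7 points, and the mixed model stayed within 0.3 of the truth.

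**If data are not missing at random.** Suppose 25% leave each arm and active leavers end at the placebo mean. The true difference is 0.75 x 21.2 = 15.9. The mixed model targets 21.2 and LOCF gives 18.5-20.1. Both are too favourable, and LOCF is the nearer.

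**The case against.** The best defence is that the plan already contains mixed models without imputation in 12.4.2, so the gap is narrow: an unnamed contrast and an unspecified covariance. Replacing the primary test in a 30-patient pilot is partly a matter of preference. This stands, and it is why a named sensitivity analysis is an acceptable minimum.

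The word conservative stands only in 12.4.2, for secondary endpoints. A reader might infer that the plan claims a conservative primary result; 12.4.1 does not say so. The label is still wrong where it appears, and it describes the same method.

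A reader might also infer that LOCF inflates the false-positive rate of this trial. The documents do not support that. The only dropout figure is 25% overall, and with balanced dropout rejection stays at 5%. A 10/40 split means 1.5 against 6 patients per arm of 15, and nothing in the plan predicts it.

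Nor can the mixed model be sold as rescuing power. With an early plateau it gains none at 25/25. At 35/15 LOCF power is 47-71% with means 41.2 and 20, but 62-78% with 21.2 and 0, against 73-74% for the model.

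Two further objections stand. The model with covariates was not itself simulated. And because 8.1 keeps assessing patients who stop drug, those with missing values have mostly left the study and its treatment, which makes missing-at-random doubtful. In that case the mixed model can be further from the truth than LOCF.

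**Conclusion.** The concern holds as one of bias and of an unsupported label. LOCF is the sole rule for the primary endpoint, and the direction of its bias cannot be known in advance. At the planned dropout, if balanced, the expected dilution is 21.2 - 20.1 = 1.1 to 21.2 - 18.5 = 2.7 points. Larger errors, or errors in favour of the drug, need unequal dropout, and their size depends on assumed means and time courses that the documents do not give. The sign changes follow from the algebra alone; the rejection and power figures rest on the simulation assumptions listed.

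This does not show that the primary test is invalid, that its type I error is inflated under the planned conditions, or that the mixed model is safe in every case. It is a worthwhile, inexpensive improvement. It does not invalidate the design.

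**What to change.** **Section 12.4.1.** Pre-specify the week 16 between-arm contrast in percent PASI reduction from the mixed model that 12.4.2 already plans.
- Use all visits in weeks 2-16, including those after study drug is stopped.
- Include arm, visit, arm-by-visit, baseline PASI and PASI stratum.
- Use visit-specific variances (for example heterogeneous compound symmetry), a named fallback (for example heterogeneous AR(1)) and Kenward-Roger degrees of freedom. Do not use homogeneous compound symmetry.
- Make this the primary estimate, with LOCF and the t-test kept as a sensitivity analysis. At the least, name it as a sensitivity analysis to the LOCF result.
- State the missing-at-random assumption and add one not-at-random sensitivity analysis, delta-adjusted or reference-based.

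**Section 12.4.2.** Delete the word conservative as a description of LOCF. Say which rule applies to a missing week 16 PASI50, since it is arguable whether the carry-forward sentence covers it. If the rule is non-response, do not call that conservative either. With equal true response p in both arms, 10/40 dropout and exit unrelated to response, it favours active by 0.3 x p, or 9 percentage points at an assumed p of 0.3.

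**Cost.** Wording only; no new visits or patients. The downsides are that the covariance must be fixed in advance for a small sample, that the model relies on missing-at-random, and that, if it becomes primary, the test is no longer the t-test behind the power statement in 12.2.
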